5.1.4 Dose Modification for management of adverse events

5.1.4.1 Dose Reduction Levels

The starting dose of regorafenib is 160 mg once daily. Study medication will be administered on a 3 weeks on/1week off schedule [3 weeks out of every 4].

Doses will be delayed or reduced for clinically significant hematologic and non-hematologic toxicities that are related to protocol therapy according to the guidelines shown in the Dose Delays/Dose Modifications table that follows. Dose modifications will

follow predefined dose levels. Dose adjustments for hematologic toxicity are based on the blood counts obtained in preparation for the day of treatment.

The modifications of regorafenib will follow the following predefined dose levels:		
Dose level 0 (standard starting dose)	160 mg po qd	Four 40-mg tablets of regorafenib
Dose level - 1	120 mg po qd	Three 40-mg tablets of regorafenib
Dose level - 2	80 mg po qd	Two 40-mg tablets of regorafenib

If a subject experiences more than one toxicity, dose reduction should be according to the toxicity with the highest grade

In the case of two or more toxicities of the same grade, the investigator may dose reduce according to that deemed most causally related to study treatment

If more than 2 dose reductions are required, regorafenib will be discontinued and patient will need to come off of the trial. If a dose reduction has been performed, intra-subject dose re-escalation can be considered (up to the maximal 160 mg daily dose) at the discretion of the treating physician provided that the toxicity(ies) has resolved to baseline.

The following tables outline dose adjustments for toxicities related to study drug except hand-foot skin reaction, hypertension and liver function test abnormalities.

Table 6-1: Recommended dose modification for toxicities except hand-foot-skin reaction, hypertension and ALT/ST/bilirubin			
NCI-CTCAE v4.0^a	Dose Interruption	Dose Modification^b	Dose for Subsequent Cycles
Grade 0-2	Treat on time	No change	No change
Grade 3	Delay until \leq Grade 2 ^c	Reduce by 1 dose level	If toxicity remains < Grade 2, dose re-escalation can be considered at the discretion of the treating investigator. If dose is re-escalated and toxicity (\geq Grade 3) recurs, institute permanent dose reduction.
Grade 4	Delay until \leq Grade 2 ^c	Reduce by 1 dose level. Permanent discontinuation can be considered at	

		treating investigator's discretion.	

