Grade 2	1 st occurrence	Consider decreasing dose by one dose level and immediately institute supportive measures. If no improvement, interrupt therapy for a minimum of 7 days, until toxicity resolves to Grade 0-1 ^{b, c}
	No improvement within 7 days or 2 nd occurrence	Interrupt therapy until toxicity resolves to Grade 0-1. ^c When resuming treatment, treat at reduced dose level ^b
	3 rd occurrence	Interrupt therapy until toxicity resolves to Grade 0-1. ^c When resuming treatment, decrease dose by one dose level. ^{b, d}
	4 th occurrence	Discontinue therapy
Grade 3	1 st occurrence	Institute supportive measures immediately. Interrupt therapy for a minimum of 7 days until toxicity resolves to Grade 0-1. ^c When resuming treatment, decrease dose by one dose level. ^{b, d}
	2 nd occurrence	Institute supportive measures immediately. Interrupt therapy for a minimum of 7 days until toxicity resolves to Grade 0-1. ^c When resuming treatment, decrease dose by one additional dose level ^{b, d}
	3 rd occurrence	Discontinue treatment permanently.

a. More conservative management is allowed if judged medically appropriate by the investigator.
 
b. If toxicity returns to Grade 0-1 after dose reduction, dose re-escalation is permitted at the discretion of the investigator if subject has completed one cycle at reduced dose without recurrence of event.
 
c. If there is no recovery after a 4-week delay, treatment with regorafenib will be discontinued permanently.
 
d. Subjects requiring > 2 dose reductions should go off protocol therapy.
 
e. The maximum daily dose is 160 mg.
		

At first occurrence of HFSR, independent of grade, prompt institution of supportive measures such as topical emollients, low potency steroids, or urea-containing creams should be administered.

Recommended prevention/management strategies for skin toxicities consistent with HFSR are summarized below:

Control of calluses

Before initiating treatment with regorafenib:

- Check condition of hands and feet.
- Suggest a manicure/pedicure, when indicated.
- Recommend pumice stone use for callus or 'rough spot' removal.

During regorafenib treatment:

- Avoid pressure points.
- Avoid items that rub, pinch or create friction.

Use of creams

- Non-urea based creams may be applied liberally.
- Keratolytic creams (e.g. urea-based creams, salicylic acid 6%) may be used sparingly and only to affected (hyperkeratotic) areas.

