3 Systolic BP \geq 160 mmHg or diastolic BP \geq 100 mmHg OR More than one drug or more intensive therapy than previously used indicated	
Treat with the aim to achieve diastolic BP \leq 90 mm Hg: Start anti-hypertensive medication
 
AND/OR Increase current anti-hypertensive medication
 
AND/OR Add additional anti-hypertensive medications.
	
 • Hold regorafenib until diastolic BP \leq 90 mm Hg, and if symptomatic, until symptoms resolve.^a • When regorafenib is restarted, continue at the same dose level. • If BP is not controlled with the addition of new or more intensive therapy, reduce by 1 dose level.^b • If Grade 3 hypertension recurs despite dose reduction and antihypertensive therapy, reduce another dose level.^c
4 Life-threatening consequences (eg, malignant hypertension, transient or permanent neurologic deficit, hypertensive crisis)	Per institutional guidelines	Discontinue therapy

a. Patients requiring a delay of >4 weeks should go off protocol therapy
 
b. If BP remains controlled for at least one cycle, dose re-escalation permitted per investigator's discretion.
 
c. Patients requiring >2 dose reductions should go off protocol therapy.
		

Liver Function Abnormalities

For patients with observed worsening of serum liver tests considered related to regorafenib (i.e. where no alternative cause is evident, such as post-hepatic cholestasis or disease progression), the dose modification and monitoring advice in Table 6-5 should be followed.

Regorafenib is a UGT1A1 inhibitor. Mild, indirect (unconjugated) hyperbilirubinemia may occur in patients with Gilbert's syndrome.

Alanine or aspartate aminotransferase (AST/ALT): for any grade increase in AST or ALT, the investigator needs to ensure that it is not due to biliary obstruction or the introduction of new drugs. Biliary obstruction should be ruled out by imaging if needed. If the elevation of AST or ALT is due to biliary obstruction, and the biliary obstruction is treated, the study drug may be restarted at the same dose level upon return of the AST and ALT to baseline or grade 2.

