For any grade increase in bilirubin, the investigator needs to ensure that it is not due to biliary obstruction or the introduction of new drugs. Biliary obstruction should be ruled out by imaging if needed. If the elevation of bilirubin is due to biliary obstruction, and the biliary obstruction is treated, the study drug may be restarted at the same dose level upon return of the bilirubin to baseline or Grade 1.

Observed elevations	1st Occurrence	Restart	Re-occurrence
ALT and/or AST >5 X ULN (≥ G3)	If patient had Grade 0 or 1 AST or ALT increase at baseline, hold the drug until AST or ALT returns to Grade 1 or baseline. If patient had Grade 2 (asymptomatic) AST or ALT increase at baseline, continue treatment at same dose and follow AST or ALT weekly for 4 weeks. Hold	Reduce one dose level and measure serum liver tests weekly for at least 4 weeks.	Discontinue

	the drug if patient develops symptoms or if AST or ALT \geq 10 x IULN; restart treatment with one dose level reduction when AST or ALT returns to baseline AND patient is asymptomatic		
ALT and/or AST > 20 X ULN (\geq G4)	Discontinue		
Bilirubin (G=2)	If patient had a normal bilirubin at baseline, hold the drug until bilirubin returns to Grade 1 or baseline If patient had Grade 1 bilirubin at baseline, continue treatment at same dose and follow bilirubin weekly for 4 weeks. Hold the drug if patient develops symptoms or if bilirubin > 2 x ULN and AST or ALT \geq 5 x ULN Restart treatment when bilirubin returns to grade 1 or baseline and patient is asymptomatic.	Restart with one dose reduction	Discontinue
Bilirubin (G=3)	Discontinue		Discontinue
During the first 2 cycles of treatment, ALT, AST and bilirubin must be monitored every 2 weeks.			

Bilirubin and AST/ALT: for any grade increase in bilirubin AST or ALT, the investigator needs to ensure that it is not due to biliary obstruction or the introduction of new drugs. Biliary obstruction should be ruled out by imaging if needed. If the elevation of AST or ALT is due to biliary obstruction, and the biliary obstruction is treated, the study drug may be restarted at the same dose level upon return of the AST and ALT to baseline or grade 2.

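### In Section 5.1.4.1 the highest-grade rule for multiple toxicities can point to no dose reduction where another toxicity's own table calls for one, because grade and dose action do not line up across tables

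*Combined protocol and SAP*

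**What the plan says.** Section 5.1.4.1 places two sentences on multiple toxicities ahead of all the dose-modification tables. The first is "If a subject experiences more than one toxicity, dose reduction should be according to the toxicity with the highest grade". The second covers ties: "In the case of two or more toxicities of the same grade, the investigator may dose reduce according to that deemed most causally related". Neither is limited to a particular table.

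The actions that matter here are in four tables of the same section:

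- **Table 6-4, Grade 3 hypertension.** Hold until blood pressure comes down, then "When regorafenib is restarted, continue at the same dose level". A reduction enters only at a later step: "If BP is not controlled with the addition of new or more intensive therapy, reduce by 1 dose level". The text introducing the table calls its reductions suggested.
- **Table 6.3, Grade 2 hand-foot skin reaction (HFSR).** For no improvement within 7 days or a second occurrence: "When resuming treatment, treat at reduced dose level". A third occurrence goes down one level. A fourth reads "Discontinue therapy". The column is headed as suggested, and a footnote allows more conservative management.
- **Liver function table (Table 6-5 in the text).** For Grade 2 bilirubin with a normal baseline, hold, then "Restart with one dose reduction"; Grade 3 bilirubin is a discontinuation. For AST or ALT above 5 x ULN, "If patient had Grade 2 (asymptomatic) AST or ALT increase at baseline, continue treatment at same dose". The introductory text says that this table's advice should be followed when the change is considered related to regorafenib.
- **Table 6-1, Grade 4 of other toxicities.** Delay and reduce by one level, with permanent discontinuation at the investigator's discretion.

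**The concern.** A rule that lets the highest grade decide is safe only if, across all tables, an equal or higher grade never carries a weaker action. Each table was built for its own toxicity, and in Tables 6.3 and 6-5 the action also depends on occurrence number or baseline grade. A Grade 3 event in one table can therefore call for less than a Grade 2 event in another. A site applying the general sentence literally and a site applying each table in turn could then dose the same patient differently, each able to cite the protocol. Section 8.1 expects 6-7 institutions, and Section 11.5 asks for conduct exactly as written except in emergencies.

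Tolerability is a secondary objective, and a patient who needs more than two reductions comes off the trial. Whether a given reduction is applied can therefore affect both the tolerability description and time on treatment.

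**Working it through.** The plan gives no figure to reproduce on this point, so the check is to set the passages side by side.

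**Step 1. Trace the combinations.**

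| Combination | Action for the higher-grade (or chosen) toxicity | Action in the other toxicity's table | Result under the multi-toxicity sentences |
|---|---|---|---|
| Grade 3 hypertension, BP controlled + first Grade 2 bilirubin, normal baseline | Same level (6-4) | One level down (6-5, to be followed) | No reduction: conflict |
| Grade 3 hypertension, BP controlled + second- or third-occurrence Grade 2 HFSR | Same level (6-4) | Reduced level (6.3, suggested) | No reduction: conflict where a new reduction would be due |
| Grade 3 hypertension, BP controlled + first Grade 3 HFSR | Same level (6-4) | One level down (6.3, suggested) | Tie; two outcomes possible: ambiguous |
| Grade 4 toxicity under 6-1 + Grade 3 bilirubin | One level down, stopping optional (6-1) | Discontinue (6-5) | Depends on whether a sentence about dose reduction reaches discontinuation: ambiguous |

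**Step 2. Check how widespread the lost reductions are.** Each row was coded by grade and by action (same dose, reduce one level, discontinue). Advice only to consider a reduction, and optional discontinuation, were not counted as called-for actions.

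Rows by grade:

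- Table 6.3: 1 at Grade 1, 4 at Grade 2, 3 at Grade 3 (8 rows)
- Table 6-4: 1 at Grade 1, 1 at Grade 2, 3 steps at Grade 3, 1 at Grade 4 (6 rows)
- Liver table: 3 at Grade 2, 4 at Grade 3, 1 at Grade 4 (8 rows)

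Cross-table pairs of unequal grade = all pairs minus equal-grade pairs:

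- 6.3 with 6-4: 8 x 6 - (1x1 + 4x1 + 3x3) = 48 - 14 = 34
- 6.3 with liver: 8 x 8 - (4x3 + 3x4) = 64 - 24 = 40
- 6-4 with liver: 6 x 8 - (1x3 + 3x4 + 1x1) = 48 - 16 = 32
- Total: 34 + 40 + 32 = 106

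In 5 of these the higher-grade row keeps the same dose while the lower-grade row calls for a reduction:

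1. Grade 3 hypertension, first step, with second-occurrence Grade 2 HFSR
2. Grade 3 hypertension, first step, with third-occurrence Grade 2 HFSR
3. Grade 3 hypertension, first step, with first Grade 2 bilirubin, normal baseline
4. AST/ALT above 5 x ULN with asymptomatic Grade 2 baseline, with second-occurrence Grade 2 HFSR
5. The same AST/ALT row with third-occurrence Grade 2 HFSR

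A further 10 pairs would lose a discontinuation, but only if the rule is read to reach discontinuations. Adding Table 6-1 brings the total to 152 pairs. It adds no lost reductions and 7 more pairs of the discontinuation type (17 in all).

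**Step 3. Limits of the count.** These are table rows, not patients, and say nothing about frequency.

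**The case against.** The strongest answer is that the rule was meant only to choose among toxicities that each call for a reduction. On that reading a hypertension restart at the same level is not a candidate, and the lost-reduction cases disappear. This is a plausible intent, but Section 5.1.4.1 does not state it. Stating it would itself be a clarification of the kind sought.

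Several narrower points stand:

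- Within Table 6-4 the action does rise with grade; the mismatch is between tables.
- Tables 6.3 and 6-4 are suggestions, so a site that reduces for HFSR breaches nothing mandatory. Only the liver table is worded as advice to be followed.
- The bilirubin case is limited to a normal baseline. With Grade 1 at baseline the table first continues the same dose, and the inclusion criteria admit bilirubin up to 2.0 x ULN.
- A patient already reduced at the first HFSR occurrence may need no new reduction at the second.
- Hypertension keeps the same level only while blood pressure is controlled.

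A reader might infer that the rule cancels a required stop, for example Grade 3 bilirubin with a Grade 4 toxicity under Table 6-1. The documents do not establish this: the sentence speaks of dose reduction, and Table 6-1 itself allows permanent discontinuation at Grade 4. Nor is the tie sentence a contradiction, since it is permissive.

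A reader might also multiply the grade 3 or worse rates in Section 1.3.2 (HFSR 17% and hypertension 7% in the colorectal trial; 56.1% and 48.5% in the GIST trial) to estimate patients affected. That would cover only the tie case. It would need independence, which is not shown, and would count events at any time rather than together. It bounds nothing.

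**Conclusion.** The point holds as an inconsistency between a general sentence and the toxicity tables. Taken as written, the highest-grade rule gives no reduction for controlled Grade 3 hypertension with a first, drug-related Grade 2 bilirubin rise from a normal baseline, whereas the liver table calls for one. Grade 2 HFSR at second or third occurrence gives a similar conflict with a suggested action, where a new reduction would be due. The tie case and the discontinuation case are ambiguities, not proven contradictions.

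The conclusion rests on reading the rule as general, which its position and wording support. How often patients would meet these combinations cannot be derived from the documents. The consequence is limited: the 6-month survival endpoint, the 39-patient design and the threshold of 16 are unaffected, and Section 8.2 reports tolerability only descriptively, without defining it by reductions or discontinuations. Different dosing between sites is a possibility that the text leaves open, not something shown to occur.

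**What to change.** Reconcile the two multi-toxicity sentences in Section 5.1.4.1 with Tables 6-1, 6.3, 6-4 and the liver function table so that each combination leads to one outcome. The revised text should state expressly whether a table's hold, reduction or discontinuation still applies when a different toxicity has an equal or higher grade. Which passage governs is a clinical decision for the sponsor's clinical team.

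The cost is about one paragraph in a protocol amendment, with no extra patients or visits. The downside is slightly less latitude for investigators. A CRF field naming the toxicity and table behind each dose change is optional, because Sections 6.2.1.2.4 and 9.1 already record the action taken for each adverse event.

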5.1.4.2 Prevention/management strategies for diarrhea

Diarrhea can be a common side effect of regorafenib. The same dose-modification algorithm used for skin toxicities can be used to address these toxicities. However, the preventive/management strategies for diarrhea should be consistent with local standards (e.g., anti-diarrheals and optimized hydration status).

Anti-diarrhea medications may be introduced if symptoms occur. Previous trials have shown that the diarrhea could be managed with loperamide. The recommended dose of loperamide is 4 mg at first onset, followed by 2 mg every 2 to 4 hours until diarrhea-free for 12 hours.

5.2 Drug logistics and accountability

All study drugs will be stored at the investigational site in accordance with Good Clinical Practice (GCP) and Good Manufacturing Practices (GMP) requirements and the instructions given by the clinical supplies department of the Institution and will be inaccessible to unauthorized personnel.

5.2.1 Accountability

The investigator, or a responsible party designated by the investigator, must maintain a careful record of the inventory and disposition of the agent (investigational or free of charge) using the NCI Drug Accountability Record or another comparable drug accountability form. (See the CTEP website at <http://ctep.cancer.gov/protocolDevelopment> for the "Policy and Guidelines for Accountability and Storage of Investigational Agents" or to obtain a copy of the drug accountability form.)

5.2.2 Destruction and Return

At the end of the study, unused supplies of regorafenib should be destroyed according to institutional policies. Destruction will be documented in the Drug Accountability Record Form. The certificate of destruction should be sent to Bayer.

A completed "Unused Study Drug Disposition Form Destruction or Return Confirmation" should be sent to Bayer at the following address:

E-mail: [contact]

OR

[contact]

OR

Mail: (VP of Medical Affairs named in contract) at
Bayer HealthCare Pharmaceuticals
[name]
[name]

5.3 Treatment compliance

An adequate record of receipt, distribution, and return of all study drugs must be kept in the form of a Drug Accountability Form.

Subject compliance with the treatment and protocol includes willingness to comply with all aspects of the protocol, and to have blood collected for all safety evaluations. At the discretion of the principal investigator, a subject may be discontinued from the trial for non-compliance with follow-up visits or study drug.

5.4 Prior and concomitant therapy

All medication that is considered necessary for the subject's welfare, and which is not expected to interfere with the evaluation of the study treatment, may be given at the discretion of the investigator. All medications (including contrast media) taken within 2 weeks prior to the start of the study and during the study must be recorded in the subject's source documentation and in the CRF (including start/stop dates, dose frequency, route of administration, and indication). Specific caution should be taken when considering or administering a concomitant medication that is metabolized by the cytochrome enzymes CYP2C8, CYP2B6 and CYP2C9. Such concomitant medication should be avoided, if possible.

Co-administration of a strong CYP3A4 inducer (rifampin) with a single 160 mg dose of Stivarga decreased the mean exposure of regorafenib, increased the mean exposure of the active metabolite M-5, and resulted in no change in the mean exposure of the active metabolite M-2. Avoid concomitant use of Stivarga with strong CYP3A4 inducers (e.g. rifampin, phenytoin, carbamazepine, phenobarbital, and St. John's Wort)

Co administration of a strong CYP3A4 inhibitor (ketoconazole) with a single 160mg dose of Stivarga increased the mean exposure of regorafenib and decreased the mean exposure of the active metabolites M-2 and M-5. Avoid concomitant use of Stivarga with strong inhibitors of CYP3A4 activity (e.g. clarithromycin, grapefruit juice, itraconazole, ketoconazole, nefazadone, posaconazole, telithromycin, and voriconazole).

Permitted concomitant therapy includes:

- Standard therapies for concurrent medical conditions.
- Supportive care for any underlying illness.
- Palliative radiation therapy is allowed if the target lesion(s) are not included within the radiation field and no more than 10% of the bone marrow is irradiated.

- Granulocyte colony-stimulating factor (G-CSF) and other hematopoietic growth factors may be used in the management of acute toxicity, such as febrile neutropenia, when clinically indicated or at the investigator's discretion. However, they may not be substituted for a required dose reduction. Subjects are permitted to take chronic erythropoietin.
- Treatment with nonconventional therapies (such as acupuncture), and vitamin/mineral supplements are permitted provided that they do not interfere with the study endpoints, in the opinion of the investigator.
- Bisphosphonates
- Subjects who are therapeutically treated with an agent such as warfarin or heparin will be allowed to participate provided that their medication dose and INR/PTT are stable. Close monitoring (day 5 of cycle 1 and day 1 of each cycle) is mandatory. If either of these values are above the therapeutic range, the doses should be modified and the assessments should be repeated weekly until they are stable.

The following are not permitted:

- Other investigational treatment during or within 21 days before starting study treatment
- Systemic antitumor therapy, including cytotoxic therapy, signal transduction inhibitors, immunotherapy, and hormonal therapy
- Bone marrow transplant or stem cell rescue
- Subjects taking narrow therapeutic index medications should be monitored proactively (e.g. warfarin, phenytoin, quinidine, carbamazepine, Phenobarbital, cyclosporine, and digoxin). Warfarin is metabolized by the cytochrome enzyme CYP2C9 and its levels may be especially affected by regorafenib
- Use of any herbal remedy (e.g. St. John's wort [*Hypericum perforatum*])

6. Procedures and variables

